Does Contrast-Enhanced
Ultrasound Positively Influence
Selection of Biopsy Sites when
Evaluating Transplant Kidneys?

NCT02625428

26 November 2014

Does Contrast-Enhanced Ultrasound Positively Influence Selection of Biopsy Sites when Evaluating Transplant Kidneys?

Protocol Date: 26 November 2014

[name], MD¹, Co-principal Investigator
[name], MD¹, Co-principal Investigator
[name], MD²
[name], MD³
[name], MD¹
[name], MD¹
[name]⁴

Introduction

Histopathological changes in kidney allograft are not always homogeneous. [1] Common pathologic abnormalities found on biopsy of transplanted organs, including renal transplants, can be patchy in distribution, especially in rejection and chronic nephropathy. [2-6] This may result in a suboptimal sample when performing a random transplant renal biopsy. [4, 6] Strategies to minimize sampling error include using larger needles or obtaining additional cores, since complications of biopsy remain very low and the benefit far exceeds the risk. [4, 6, 7] We hypothesize that contrast-enhanced ultrasound (CEUS) may help evaluate segmental differences in renal perfusion better than Doppler Ultrasound and thus help direct the biopsy to the most abnormal part of the renal cortex. This should maximize detection and increase the odds of demonstrating the true grade/severity of the histopathological abnormality.

CEUS has been FDA approved for echocardiography but its use elsewhere in the body is considered off-label. It has been used extensively outside the United States within the abdomen, but most commonly for liver masses. CEUS investigations within transplant kidneys have shown additional information can be obtained when compared to gray-scale and Doppler ultrasound. Apart from a better estimate of parenchymal perfusion it allows for evaluation of graft vascular kinetics, including quantitative measurements, e.g. time-to-peak enhancement (TTP) within the cortex or pyramids. [8-14] Studies have also shown CEUS is more sensitive to renal perfusion defects than Tc-DTPA. [15] This ability of CEUS to evaluate perfusion over time may help target renal transplant biopsies to the most abnormal segments.

Hypothesis/Expected Results

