CEUS targeted biopsies to areas of decreased or inhomogeneous perfusion will show disease processes significantly more often or of a higher severity than (non-targeted) random biopsies. Additionally, this directed biopsy may demonstrate more significant or advanced disease, as measured by Banff criteria, when compared to a routine non-targeted biopsy. Random biopsies

of different segments in the same kidney, when no focal or segmental CEUS abnormality is demonstrated, will not be significantly discordant for disease or Banff criteria.

Proposed investigation

IRB approval from our institution will be obtained for this pilot study of 40 consecutive consenting male and female adult patients over 18 years of age undergoing renal transplant ultrasound-guided percutaneous biopsy within 24 months post-transplant, including patients undergoing biopsy to evaluate a recent rise in serum creatinine, so-called for cause biopsies and patients undergoing routine protocol (surveillance) biopsies without other evidence of renal dysfunction. Pregnant patients will be excluded. The routine protocol biopsies are done at 4 months and 1 year after transplant mostly looking for subclinical rejection. Informed written consent (IRB approved consent form) will be obtained from all patients prior to the scan and biopsy procedure. This will include consent for the off-label use of Optison and the need to obtain 2 or 3 biopsies specimens, when routinely only 1 or 2 are obtained. All patients will meet our standard anticoagulation guidelines for undergoing renal transplant biopsy.

CEUS will be performed in addition to our routine color-Doppler ultrasound evaluation of the transplant kidney prior to the biopsy. One vial (3.0 mL) of Optison will be utilized for each patient, with expected doses to be in the range of 1-1.5 mL for each scan sequence, allowing up to 2 to 3 scan sequences per patient exam. Low mechanical index settings and coded harmonics will be utilized. Each scan sequence will be recorded for up to 5 minutes. Post-processing will be performed using an off-line workstation if needed.

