It is standard practice that patients be kept for observation 1 hour post biopsy and called by the nurse at 24 hours. Those patients participating in the study will also be called 72 hours post procedure. Any complications or adverse effects occurring within 1 week of the procedure will be recorded.

When an adverse event has been identified, the study team will take appropriate action necessary to protect the study participant and then complete the Study Adverse event Worksheet and log. The investigator will evaluate the event and determine the necessary follow-up and reporting required.

The investigator will report to the Mayo IRB any UPIRTSOs and Non-UPIRTSOs according to the Mayo IRB Policy and Procedures.

Data Handling and Statistical Analysis

All data will be entered into a secure database and anonymized. The statistician will create REDCap electronic data forms. Statistical analysis will be performed by our statistician after data has been obtained for all 40 patients. Detection rates would be compared by using the McNemar test. Based on our last 50 renal transplant biopsies, 84% were “surveillance” and 16% were “For Cause”. Positive rejection rates have been reported at 12-61% (1 month survey at MCA = 16% rejection) for the surveillance group [18-20] and 25-46% (1 month survey at MCA= 25% rejection) for the For Cause group. [20, 21] Using 12% and 25% as the baseline rate of rejection detected for Protocol and For Cause biopsies, respectively, we expect 17% of random biopsies to be positive for rejection ($0.25 \times 0.16 + 0.16 \times 0.84 = 0.17$). Conservatively, assuming a 10% false negative rate by CEUS biopsy, a sample of 40 patients has 80% power (alpha .05) if detection increases by 20 percentage points from 17% to 37%.

Ethical Considerations

This study is to be conducted according to United States government regulations and Institutional research policies and procedures. The investigator will ensure that the basic principles of “Good Clinical Practice,” as outlined in Title 21 of Code of Federal Regulations (CFR), Part 50, “Protection of Human Subjects”; 21 CFR, part 54, “Financial Disclosure by Clinical Investigators”; 21 CFR, part 56, “Institutional Review Boards”; and 21 CFR, Part 11, “Electronic Records, Electronic Signature,” are adhered to.

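### Adverse events are to be logged for one week, but no way of finding them is stated after the 72-hour call, so events on days 4 to 7 may be missed

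*Combined protocol and SAP*

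**What the plan says.** Three consecutive statements in the protocol's Safety and Adverse Events section set out the follow-up. Routine care comes first: "It is standard practice that patients be kept for observation 1 hour post biopsy and called by the nurse at 24 hours". The study adds one contact: "Those patients participating in the study will also be called 72 hours post procedure". The recording window follows: "Any complications or adverse effects occurring within 1 week of the procedure will be recorded".

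The next paragraph deals with events already known: "When an adverse event has been identified, the study team will take appropriate action necessary to protect the study participant". It then covers the worksheet and log, the investigator's evaluation and reporting to the IRB. It does not say how an event after 72 hours would come to the team's notice.

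Under Data Handling and Statistical Analysis, the only comparison named is for detection: "Detection rates would be compared by using the McNemar test". No complication rate is defined and no safety analysis is planned.

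**The concern.** The recording window is longer than the period of planned contact, and nothing in the protocol bridges the difference. If the schedule is followed exactly as written, days 4 to 7 have no systematic capture of events.

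This matters because the study adds exposure. The contrast agent is used off-label, and the Proposed investigation section says that consent will cover "the need to obtain 2 or 3 biopsies specimens, when routinely only 1 or 2 are obtained". The Introduction supports taking additional cores on the ground that complications are rare: "since complications of biopsy remain very low and the benefit far exceeds the risk". The study's own event log is likely to be read as evidence on that premise. Expected Deliverables foresees publication, transfer of the anonymized data to the company supplying the contrast agent, and possibly a larger study. A log labelled as covering one week, but actively collected for three days, would carry that label into each of these uses. Any error from unfound events goes in one direction, towards too few.

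**Working it through.** The protocol states no complication rate, safety sample size or safety power, so there is no figure of its own to reproduce. The check has three steps.

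**1. Coverage of the window** (inputs from Safety and Adverse Events)

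- Window: 7 × 24 = 168 hours.
- Last scheduled contact: 72 hours.
- Remainder: 168 − 72 = 96 hours, and 96/168 = 57%. Planned contact reaches 72/168 = 43% of the window.

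**2. Share of one-week events captured**

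Let *f* be the share of one-week events that arise or are first noticed after 72 hours, and *s* the share of those that are found anyway. Then captured share = 1 − *f*(1 − *s*). The protocol gives neither quantity, so every value below is an assumption.

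| *f* | *s* = 0 | *s* = 0.5 | *s* = 1 |
|---|---|---|---|
| 0 | 100% | 100% | 100% |
| 5% | 95% | 97.5% | 100% |
| 20% | 80% | 90% | 100% |
| 57% (constant hazard over the week) | 43% | 71% | 100% |

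**3. Expected number of events missed among 40 patients**

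Missed = 40 × *p* × *f* × (1 − *s*), where *p* is the true one-week rate, also assumed. With *s* = 0:

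| *p* | Expected events (40 × *p*) | Missed, *f* = 20% | Missed, *f* = 57% |
|---|---|---|---|
| 1% | 0.4 | 0.08 | 0.23 |
| 5% | 2 | 0.4 | 1.1 |
| 10% | 4 | 0.8 | 2.3 |

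One missed event changes an observed proportion by 1/40 = 2.5 percentage points.

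**The case against.** The strongest reply is that a recording window and a contact schedule do different jobs. The window says which events belong in the log, and the calls are a minimum of active contact. A window that outlasts the last call is not a contradiction, and this is a 40-patient pilot that already adds a call to routine care. That is fair, and the point is not put as a contradiction. But the reply leaves open how an event on day 5 reaches the log.

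Four stronger readings are tempting and are not supported:

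- **That late events rest on spontaneous reports.** A reader might infer this, but the protocol is silent. Routine care contacts and record review are neither described nor excluded, and nephrology is among the study departments.
- **That the count will be too low.** This needs events that arise or are noticed after 72 hours and are then not found. With *f* = 0 or *s* = 1 nothing is lost. Only the possibility is supported.
- **That 57% measures the bias.** It is a share of calendar time. It equals the share of events missed only with a constant hazard and no late capture. Exact 95% upper limits for 40 patients (8.8% for no events, 13.2% for one) do not measure the bias either. They reflect the sample size and would be the same with complete day-7 follow-up.
- **That a planned endpoint is biased.** No one-week complication rate is defined or analysed. Both cores come from the same patient, so the McNemar comparison of detection is untouched.

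It would also be too strong to say that every patient has an extra core. Support Requested from GE budgets one further sample per patient, but routine practice is sometimes two cores and the study minimum is two.

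**Conclusion.** The point holds as a gap in safety ascertainment. The protocol promises recording to one week, schedules its last contact at 72 hours, and states no method for finding events in the remaining 96 of 168 hours. Events on days 4 to 7 may be missed, and any descriptive one-week safety statement may be too low.

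The size is unknown. Under the assumptions shown, capture runs from 43% to 100%, and the expected number missed runs from none to about 2.3 events in the whole study. The upper end needs a true rate of 10%, a constant hazard and no late capture. With a true rate of 1% to 5%, 20% late onset and none of those found, it is 0.08 to 0.4 events. The conclusion that a gap exists rests only on the text and on none of these assumptions.

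This is a cheap improvement and no threat to the main result. Sample size, power and the detection comparison are unaffected.

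**What to change.** Add to Safety and Adverse Events a day-7 check for each patient, either a scripted call or a systematic record review, carried out by the existing team and used to close that patient's adverse-event log. Planned coverage of the window then rises from 43% to 100%. The cost is about 40 short calls or record checks.

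If that is not wanted, change the wording: describe complications as actively followed to 72 hours, list later events separately, and state how they came to light. If routine contacts or record review already cover days 4 to 7, one sentence saying so would be enough, provided the review is done for every patient.

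### The sample-size sentence declares a 12% surveillance rejection rate but its equation uses 16%, so the baseline is 14% or 17% depending on which is read; power hardly moves

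*Combined protocol and SAP*

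**What the plan says.** All the relevant text is in the protocol's Data Handling and Statistical Analysis section.

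- Case mix, from the centre's last 50 transplant biopsies: "84% were “surveillance” and 16% were “For Cause".
- Surveillance rejection rate: "Positive rejection rates have been reported at 12-61% (1 month survey at MCA = 16% rejection) for the surveillance group".
- For-cause rejection rate: "25-46% (1 month survey at MCA= 25% rejection) for the For Cause group".
- Rates declared for planning: "Using 12% and 25% as the baseline rate of rejection detected for Protocol and For Cause biopsies".
- Resulting baseline: "we expect 17% of random biopsies to be positive for rejection", supported by the equation "0.25 \times 0.16 + 0.16 \times 0.84 = 0.17".
- Power statement: "Conservatively, assuming a 10% false negative rate by CEUS biopsy", followed by "a sample of 40 patients has 80% power (alpha .05) if detection increases by 20 percentage points from 17% to 37" percent.

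The comparison is a McNemar test on paired cores. The section does not say whether alpha is one- or two-sided, or what the 10% false-negative rate is a percentage of.

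**The concern.** The equation weights two rates by the case mix. Its first term, 0.25 × 0.16, is the for-cause rate times the for-cause share. Its second, 0.16 × 0.84, is therefore the surveillance rate times the surveillance share, and the rate entered there is 16%. The words of the same sentence say 12%. The number 0.16 does two jobs in the equation, as a case-mix share and as a rejection rate, so the mismatch is easy to miss.

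The 17% is the baseline to which the 20-point rise is added to reach 37%, and this is the only sample-size justification in the protocol. A reader cannot reproduce it from the rates the sentence declares. The Expected Deliverables section says the pilot may lead to a larger study, so an unresolved baseline could be carried into later planning.

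**Working it through.** **1. The plan's own figure.** Inputs as printed: for-cause rate 0.25, for-cause share 0.16, surveillance rate 0.16, surveillance share 0.84.

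0.25 × 0.16 + 0.16 × 0.84 = 0.0400 + 0.1344 = 0.1744, which rounds to 17%. The equation is arithmetically correct for a 16% surveillance rate.

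**2. The declared rates.** The same shares with 12% and 25%:

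0.25 × 0.16 + 0.12 × 0.84 = 0.0400 + 0.1008 = 0.1408, about 14%.

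The gap is 0.1744 − 0.1408 = 0.0336, or 3.4 points, which is too large for rounding. In 40 patients the expected random-core positives are 40 × 0.1744 = 7.0 or 40 × 0.1408 = 5.6. Adding the stated 20 points gives 17% to 37%, or 14% to 34%.

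**3. Effect on power.** Let c be the proportion of patients with a positive random core and a negative targeted core (the opposite discordant cell), d = 0.20 the rise, and b = c + d the other discordant cell. The two-sided normal approximation for McNemar's test with N = 40 is

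power = Φ{ (d√N − 1.96√(b + c)) / √(b + c − d²) }.

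For 17% to 37% with c = 10% of the baseline: c = 0.017, b = 0.217 and b + c = 0.234. The numerator is 1.265 − 1.96 × 0.4837 = 0.317 and the denominator is √0.194 = 0.4405. The ratio is 0.719 and the power 76.4%.

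The protocol does not define c, so the values below are assumptions, shown as a range.

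| Opposite cell c | 17% to 37% | 14% to 34% |
|---|---|---|
| 0 | 83.4% | 83.4% |
| 10% of the baseline rate | 76.4% | 77.6% |
| 10% of the target rate | 68.9% | 70.0% |
| 10% of all patients | 51.7% | 51.7% |

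Once d is fixed, the baseline enters only through the way c is set. It changes power by 0 to about 1 point. With the exact two-sided test and c at 10% of the baseline, the figures are 72.3% and 74.1%, a difference of just under 2 points.

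**4. Can the stated 80% show which baseline was used?** No. One-sided, with c at 10% of the target rate, power is 79.8% for 17% to 37% and about 80.6% for 14% to 34%. Both round to about 80%, so working back from the power figure does not separate the two baselines.

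**The case against.** The strongest reply is that the equation, the 17% and the step from 17% to 37% all agree with each other and with the local survey rates of 16% and 25% given just before. On that view only the 12% in the words is out of line, and the defect is one mistyped number. This stands as a plausible account, but the text does not establish it. The 12% is the low end of the reported surveillance range, just as 25% is the low end of the for-cause range, so the pair 12% and 25% is also a coherent choice. The 25% is both a low end and a local survey value, so it does not help to decide. Both numbers are legible, and nothing elsewhere in the protocol resolves the conflict.

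It can also be said that this is a pilot of 40 consecutive patients, and that the planning baseline enters neither the McNemar analysis nor any estimate. That is right, and it limits the severity.

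Three stronger readings are tempting, and the documents do not support them:

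- A reader might infer that the 17% is simply wrong. It follows correctly from the 16% and 25% in the same section.
- A reader might infer that a 14% baseline with 37% kept as the target demands a 23-point rise (power about 84% with c at 10% of the baseline). The protocol fixes the effect at 20 percentage points, so the target would move with the baseline.
- A reader might carry over the relative gain instead: 37/17 = 2.18-fold, so 14% becomes about 30.5% and power about 67% on the same assumption. The protocol states the effect in absolute points, not as a ratio.

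**Conclusion.** The point holds as an internal inconsistency: the sentence declares 12% and its equation uses 16%. The baseline is 14% on the first and 17% on the second, and the documents do not say which was meant.

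It corrects a stated planning figure. It does not by itself show that 40 patients is the wrong number, although a reader might infer that from an error in the only power statement. The small effect on power rests on holding the 20-point rise, on a two-sided 5% test, and on the assumed values of the opposite discordant cell. The spread across those values (83.4% down to 51.7%) is far larger than the effect of the baseline. The undefined sidedness and false-negative denominator therefore matter more to the 80% claim than the choice between 12% and 16%. That is a separate question, but it is why the power must be restated whichever rate is kept. Severity is minor to moderate.

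**What to change.** Use one surveillance rate throughout the paragraph. The sponsor should confirm which was intended and then make one of two changes:

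- If 16% was meant, change the declared rates to 16% and 25% and say that they come from the local survey. The equation, the 17% and the 17% to 37% alternative stay.
- If 12% was meant, put 0.12 in the equation, so that 0.25 × 0.16 + 0.12 × 0.84 = 0.14, and restate the baseline as 14% and the alternative as 14% to 34%, keeping the 20-point rise.

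In either case, rerun and restate the McNemar power at 40 pairs. Give the sidedness of alpha, the form of the test, and the opposite discordant cell assumed, including what the 10% false-negative rate is a percentage of. Keeping 16% does not remove the need for the rerun, since the 80% is not reproduced for 17% to 37% under most of the readings above.

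The cost is one sentence in the protocol and one short calculation. Nothing in the conduct of the study changes.
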